4.3 Handling of repeated and unscheduled measurements

All repeated and unscheduled measurements will be presented in the data listings, where applicable. The following general rules will apply to all repeated and unscheduled measurements:

- For repeated measurements obtained prior to the first dose of study medication the latest value (which may be scheduled or unscheduled) will be used in the calculation of the descriptive statistics
- For repeated measurements obtained at the designated Baseline visit, the latest value (which may be scheduled or unscheduled) will be defined as the Baseline provided that this occurred prior to the first dose of study medication
- Unscheduled and repeated measurements will not be used in the descriptive statistics at time points after first dose of study medication
- Unscheduled measurements performed for the Early Withdrawal (EW) visit will be assigned to the EOS Visit (Section 4.4) and analyzed accordingly as an EOS Visit.

Handling of measurements obtained at the early withdrawal 4.4 visiť

Study participants who withdraw early from the study for any reason, including those withdrawn from study medication, will be asked to return for the EOS Visit 7 to 9 days after last intake of study medication and will then enter the SFU Period and will undergo the same assessments performed at the EOS Visit.

his docul Not applicable. Interim analyses and data monitoring

Multicenter studies

This study is planned to be conducted at sites in Netherlands, Bulgaria and Germany (and potentially other countries in Europe). However, there is no plan to explore sites effect in the analysis.

4.7 Multiple comparisons/multiplicity

Not applicable.

4.8 Use of an efficacy subset of subjects

Not applicable.

S any extensions or variations thereof. 4.9 Active-control studies intended to show equivalence

Not applicable.

4.10 Examination of subgroups

Not applicable.

STUDY POPULATION CHARACTERISTICS 5

Subject disposition 5.1

The number of participants who were enrolled into the study, participants who completed or prematurely discontinued the study, as well as the reason for discontinuation will be summarized for all participants, based on the ES. A participant who completed the study is defined as a study participant who completed all visits up to and including the SFU.

The number and percentage of study participants who discontinued due to AEs will be summarized separately for all study participants, based on the ES. This will be used for European Union Drug Regulating Authorities Clinical Trials (EudraCT) reporting.

The number and percentage of study participants included in each of the analysis sets will be summarized for all participants and for each treatment group based on the ES. Percentages will be calculated based on the ES for the purpose of this summary.

Screen failure reasons will be summarized for the ES. A listing of subjects who did not meet study eligibility criteria will also be presented for the ES.

In addition, the following listings will be presented:

- Subject disposition (ES) •
- Study discontinuation (FAS)
- Visit dates (FAS)
- Subject analysis sets (ES) •

The listing of subject disposition will include the date of informed consent, date and time of first and last dose of study medication, date of premature termination and primary reason (if applicable) and date of final contact.

The listing of study discontinuation will include the reason for discontinuation and the number of days on study medication.

The number of days on study medication will be calculated as follows:

This doci

Number of Days on study medication

= (Date of Last Dose Received – Date of First Dose Received) + 1

5.2 Protocol deviations

Important protocol deviations will be identified and classified by the deviation types in the IPD document.

ions thereof A listing of all IPDs identified at the DEM will be presented for all subjects based on the FAS and will include the deviation type and description. The number and percentage of subjects in the FAS with IPDs will be summarized for all subjects, for each treatment period and for each deviation type. The denominator for the percentages will be the number of subjects in the FAS.

rd any exter DEMOGRAPHICS AND OTHER BASELINE 6 **CHARACTERISTICS**

6.1 **Demographics**

A by-subject (study participant) listing of demographics will be presented based on the ES. This will include the date of birth, age (in years), sex, race, ethnicity, height (in cm), weight (in kg) body mass index (BMI, in kg/m^2). The body weight will be the measurement obtained at Screening.

Body mass index (kg/m^2) is calculated based on the height (in m) and the weight (in kg) using the following formula:

BMI $(kg/m^2) = weight (kg)/[height (m)]^2$

The BMI will be reported to 1 decimal place?

All demographic characteristics (except for date of birth) will be summarized for all participants based on the FAS. The summary of age will include descriptive statistics and categorical summaries, the latter based on requirements for European Union Drug Regulating Authorities Clinical Trials (EudraCT) and clinicaltrials.gov reporting.

For the EudraCT reporting, the categories will include:

- 18 to <65 years
- 65 to <85 years
- ≥85 years

For clinicaltrials.gov reporting, the categories will include:

 ≤ 18 years

19 to <65 years

 ≥ 65 years

Disease baseline characteristics will be also summarized for the FAS, including AED characteristics (name, dosage, frequency).

6.2 Other Baseline characteristics

Lifestyle information (alcohol, tobacco, illicit drug use and caffeinated beverage use), C-SSRS and Epilepsy characteristics (duration of epilepsy, seizure clusters history, status epilepticus

Index of all participants in the FAS. Index of all participants in the FAS. Index of all participants in the Isted and summarized (in an incidence table) for the FAS for all participants, by MedDRA system organ class (SOC) and preferred term (PT). The reported term will be included in the listing. The summary will include the number and percentage of study participant, and will be sorted alphabetically by SOC and by descending each SOC, based on the 'All Subjects' column Procedure bisto

Procedure history will be listed separately by the procedure reported term based on the FAS. Concomitant medical procedures occurring during the study will be listed for the FAS.

8 EFFICACY ANALYSES

Not applicable.

9 PHARMACOKINETICS

The calculation of the PK parameters of PSL and its metabolites (

for both plasma conventional venous and MITRA dried blood) will be performed by the Quantitative Clinical Development Department, ICON PLC, All PK TFLs will be produced by ICON PLC SAS programming (Early Phase).

Pharmacokinetic concentrations and PK parameters will be summarized by treatment i.e. PSL with OXC (Group 1) and without OXC (Group 2), using the PK-PPS and listed on the FAS by treatment and study participants. Figures of summaries will be based on the PK-PPS and figures of individual concentrations will be based on the FAS.

Pharmacokinetic parameters of PSL and metabolites and for both plasma conventional venous and MITRA dried blood) will be calculated using the actual blood sampling times.

Analysis of the primary pharmacokinetic variables 9.1

Individual plasma concentrations of PSL (from conventional venous sampling and MITRA microsampling) will be listed by treatment group and will include the actual and nominal sampling times and the deviation between them. All deviations will be calculated relative to the first dose of study medication. Any samples that are obtained outside the tolerance window permitted at the specified time point will be discussed at the DEM and any possible exclusion from analysis will be documented accordingly. The primary PK variables in plasma used for PSL and metabolites () are: C_{max} , t_{max} , and AUC_{τ} . In and addition, CL/Fss will be evaluated for PSL only. Cmax and tmax will be determined from the observed concentration and time data. When two or more identical peak concentrations are observed, t_{max} will be defined as the time of the first occurrence. AUC_t will be computed using the linear trapezoidal rule.

The PK plasma and dried blood concentrations and the primary PK parameters of PSL and its metabolites from plasma and dried blood will be summarized by treatment group and nominal sampling times using descriptive statistics (number of available observations [n], arithmetic mean, median, SD, minimum, maximum, geometric mean, geometric CV and 95% CI for the geometric mean [assuming lognormally distributed data]). Values below the LLOQ will be reported with a clear sign (flag variable in the dataset) indicating that they were below the LLOO.

Individual participant concentration-time profiles of PSL, from conventional venous sampling and MITRA microsampling will be displayed graphically in linear and semi-logarithmic scale.

this do

Combined individual (spaghetti) plots will be displayed by treatment group with all participants overlaid on the same plot (linear and semi-logarithmic scale).

All plasma concentration figures will include the LLOQ on the semi-logarithmic scale plots and the will be based on scheduled times. The primary comparison of interest is the similarity of -1 (Traci Geometric mean profiles of plasma concentrations for PSL over time will be presented, with all

(Treatment Group 2). Pharmacokinetic parameters (C_{max} and AUC_{τ}) of PSL will be compared between the 2 treatment groups (Group 1 [Inducers] vs. Group 2 [Neutral {control}]) using analysis of variance (ANOVA) with treatment group fitted as fixed effects. Roint estimates for the ratio of geometric means with and without OXC (Group 1 [Inducers] vs Group 2 [Neutral {control}])) and the respective 2-sided 90% CIs will be computed using the least squares means and the root mean squares of error from the mixed effects model, based on the log-transformed data with subsequent exponential transformation. Additional exploratory analyses may be conducted using subgroups of the 2 treatment groups (monotherapy subgroups, adjunctive subgroups).

Analysis of secondary pharmacokinetic variables 9.2

Pharmacokinetic parameters (Cmax, AUCt) of PSL metabolites will be compared between the 2 treatment groups (Group 1 [Inducers] vs Group 2 [Neutral {control}]) using analysis of variance (ANOVA) on the log-transformed parameters.

The ANOVA model described in Section 9.1 will be applied for the PK variables (C_{max}, and AUC_{τ}) for the two PSL metabolites and) in plasma (conventional venous sampling). Roint estimates for the ratio of geometric means and the respective 2-sided 90% CIs will be computed using the least squares means and the root mean squares of error from the mixed effects model, based on the log-transformed data with subsequent exponential transformation for the same comparisons than those described in Section 9.1.

Additionally, Cmax, tmax, AUC_t, for PSL metabolites (and) and the ratio of metabolite to PSL based on AUC τ will be summarized descriptively. Metabolite to parent ratios will be corrected for molecular weight. The molecular weight (MW) is 419, the MW of metabolite of PSL is 432.8, the MW of metabolite

is 433. All secondary variables including trough plasma concentration of MHD (OXC metabolite) before, during, and after dosing to steady state with PSL will also be listed.

This docut 9.3

Analysis of other pharmacokinetic variables

The other PK parameters and their analysis are the following:

The blood concentrations and blood PK variables for PSL and its metabolite based on the MITRA microsampling will be summarized and plotted as described in Section 9.1.

- The PSL concentrations and PK parameters obtained from MITRA microsampling method will be summarized as those obtained from the venous sampling method and compared with those of the conventional venous sampling method using descriptive analysis (tables with summary statistics and graphs).
- ions thereof As exploratory analysis, point estimates for the ratio of geometric means for the PK parameters C_{max} , and AUC_t for PSL based on the MITRA microsampling compared to the plasma conventional venous sampling along with the 2-sided 90% CIs will be computed using the least squares means and the root mean squares of error from a specific linear mixed sionsor effects model, based on of the log-transformed data with subsequent exponential transformation for the following:
 - 0 Overall: conventional venous compared to MITRA
- Scatter plots of the MITRA dried blood concentrations versus venous plasma concentrations for PSL and its metabolite will be presented. The correlation between two measurements (conventional vs. MITRA) of PSL and its metabolites concentration will be evaluated using linear regression, considering conventional sample concentration as independent variable and MITRA sample concentration as dependent variable. Furthermore a Bland-Altman plot of the differences in concentration between MITRA dried blood and venous plasma vs. true measurement (average of MITRA dried blood with venous plasma) concentrations for PSL and its metabolite including regression line and its 90% confidence intervals will be presented for the log transformed data.
- The predose trough concentrations for both plasma conventional venous and MITRA dried blood sampling methods will be listed separately. The trough PSL concentrations will be summarized by treatment group and day. Geometric mean along with their 95% CI for the trough concentrations will be plotted against time.
- Trough plasma concentrations of **DEV**, LTG, or BRV before, during, and after dosing to steady state with PSL

SAFETY ANALYSES 10

All safety summaries and listings will be performed using the FAS. Unless stated otherwise, all summaries including figures will be presented by treatment group (Group 1 and Group 2) as detailed in the shells for figures (Table 13-1)Table 13-1. Summaries for continuous variables by timepoint will be based on the averaged value across the treatment group. Categorical variables will be summarized according to the actual group (no pooling).

10.1 **Extent of exposure**

All study medication administration details will be listed by treatment group and study participant. The listing will include the date and time of administration of the morning and evening dose, depending on the treatment group, (either PSL and/ or OXC) and total daily dose of both medications.

Exposure data will be listed only.

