5.3.1 Venous blood

Venous blood samples for PK analysis will be collected as follows:

- Padsevonil and PSL metabolites (
 - prior to the morning dose of PSL on Day 1 through Day 7 and Day 9 through Day 13

and

):

- prior to the morning dose of PSL and 0.25h, 0.5h, 1h, 1.5h, 2h, 3h, 4h, 6h, 8h, and 12h after administration of the morning dose of PSL (prior to the evening dose) on Day 8
- AEDs: trough samples prior to the morning dose of the AED(s) on Day -1, Day 1 through Day 13, and the EOS Visit

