5.3.2 Microsamples of capillary blood

Samples for PK of PSE from a finger skin prick will be collected using the MITRA device, as close to the conventional PK sampling as possible, at each of the time points identified for the venous blood samples for Day 8 in Section 5.3.1.

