- nd any extensions or variations thereof. - Approximately 0.5h prior to PSL morning dose, and 0.5h, 1h, 2h, 3h, and 6h after the morning dose
- Blood samples (venous) for trough PK analysis (prior to AED morning dose):
 - MHD plasma level (only for study participants taking OXC)
 - AED trough level (for storage)
- Blood samples (venous and MITRA) for PK analysis (relative to PSL morning dose):
 - PSL and metabolites (and) PK profile analysis (predose [within 5 minutes of dosing], 0.25h, 0.5h, 1h, 1.5h, 2h, 3h, 4h, 6h, 8h, and 12h [to be obtained prior to evening dose])
- **Dispense** PSL •
- Recording of AEs/medical procedures

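### SAP 9.3 puts a 90% CI on a Bland-Altman line through repeated MITRA/venous pairs with no participant effect named, and specifies no limits of agreement

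*SAP*

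**What the plan says.** Protocol 5.3.1 sets the Day 8 venous samples for padsevonil (PSL) "prior to the morning dose of PSL and 0.25h, 0.5h, 1h, 1.5h, 2h, 3h, 4h, 6h, 8h, and 12h" after that dose, which is 11 time points. Protocol 5.3.2 asks for a MITRA finger-prick sample "at each of the time points identified for the venous blood samples for Day 8 in Section 5.3.1". The planned sample size is 28 participants (Protocol 12.8).

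SAP 9.3 then compares the two methods at two levels.

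- **PK parameters.** For Cmax and AUCtau of PSL, a MITRA-to-venous ratio of geometric means with a 90% CI comes from a linear mixed effects model. SAP 3.9 declares this as an addition to the protocol, whose Section 12.3.3 plans a descriptive comparison only.
- **Individual concentrations.** The correlation between methods is evaluated by "linear regression, considering conventional sample concentration as independent variable and MITRA sample concentration as dependent variable", with no interval stated. There is also a "Bland-Altman plot of the differences in concentration between MITRA dried blood and venous plasma", drawn against the average of the two values. The SAP adds that the "regression line and its 90% confidence intervals will be presented for the log transformed data".

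For the concentration-level items the SAP names no participant effect, repeated-measures structure, clustered error or bootstrap. It does not mention limits of agreement.

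**The concern.** The log-difference between a MITRA value and its venous pair compares whole blood with plasma. A participant's blood-to-plasma ratio, and anything systematic in how that participant's finger-prick samples were taken, enters all of that participant's pairs. Positive within-participant correlation of the differences is therefore to be expected. A line fitted to the pooled pairs counts each pair as new information and reports an interval that is too narrow around the average bias. The SAP names a mixed model for the PK parameters, where each participant supplies one pair per parameter, but not for the concentrations, where each supplies up to 11.

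The second gap is in what the plot reports. A CI for a regression line gives the precision of the average trend. It does not show how far an individual MITRA result may lie from its venous pair, which is what limits of agreement describe. As specified, the plot could show a tight band around the mean bias and leave the scatter of individual differences unquantified.

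**Working it through.** **The documents' own figure.** No precision or sample-size figure is given for the MITRA comparison. The only one is 92% power for the primary AUCtau comparison. With CV 50%, the log-scale SD is sqrt(ln(1 + 0.5^2)) = 0.472. The difference is ln(1.75) = 0.560, with 14 per group and one-sided alpha 0.05. The noncentral t distribution gives 92.0%, so the figure reproduces. Its use here is to supply a between-participant log SD of 0.47 for the slope check.

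**Inputs**
- Pairs per participant, m = 1 predose + 10 postdose = 11 (Protocol 5.3.1, 5.3.2).
- Participants, K = 28, so at most 28 x 11 = 308 pairs per analyte.
- rho, the within-participant correlation of the log-differences: not in the documents, so assumed from 0 to 0.7.

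**Centre of the line.** Let the log-difference have total variance s^2, with rho*s^2 between and (1 - rho)*s^2 within participants.

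- Pooled least squares reports a variance for the mean of s^2/308.
- The actual variance is [rho*s^2 + (1 - rho)*s^2/11]/28 = s^2*(1 + 10*rho)/308.
- The true SE is therefore sqrt(1 + 10*rho) times the reported SE.
- Approximate coverage of the nominal 90% CI is 2*Phi(1.645/sqrt(1 + 10*rho)) - 1.

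This was checked by simulation: 28 x 11 pairs, 3000 runs per setting, zero true bias, between-participant log SD 0.47, total SD of the log-difference 0.2 and a one-compartment steady-state profile. The last two are assumptions.

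| rho | True SE / reported SE | Effective pairs, 308/(1 + 10*rho) | Coverage, formula | Coverage, simulated |
|---|---|---|---|---|
| 0 | 1.00 | 308 | 90% | 90% |
| 0.05 | 1.22 | 205 | 82% | 82% |
| 0.1 | 1.41 | 154 | 76% | 76% |
| 0.3 | 2.00 | 77 | 59% | 61% |
| 0.5 | 2.45 | 51 | 50% | 50% |
| 0.7 | 2.83 | 38.5 | 44% | 43% |

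The SE ratio depends on m and rho, not on K. Drawing the plot by treatment group (14 x 11 = 154 pairs) would leave it unchanged.

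**Slope of the line.** The same simulation gives a less settled picture.

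| Between-participant log SD of concentration | rho | True SE / reported SE | Coverage of nominal 90% CI |
|---|---|---|---|
| 0.47 (from CV 50%) | 0.1 | 1.14 | 86% |
| 0.47 | 0.3 | 1.30 | 79% |
| 0.47 | 0.5 | 1.49 | 73% |
| 0.1 | 0.3 | 0.88 | 94% |
| 0.1 | 0.5 | 0.81 | 96% |
| 0.9 | 0.3 | 1.64 | 68% |
| 0.9 | 0.5 | 1.94 | 61% |

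When concentrations vary mainly within participants, the slope is estimated mostly from within-participant contrasts. The pooled residual still carries the between-participant variance, so the reported slope SE is then too large.

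**Limits of agreement.** These cannot be computed in advance, because the documents give no variance for the differences.

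**The case against.** The strongest reply is that little hangs on this analysis. Protocol 4.1.3 lists the comparison among the other PK variables and Protocol 12.3.3 plans it as descriptive. No acceptance limit, test or decision is tied to the Bland-Altman line. The Cmax and AUCtau ratios already come from a mixed model. All of that stands, and it sets the severity.

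Several stronger readings are tempting, and the documents do not support them.

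- **That the SAP declares the pairs independent.** It is silent. Pooled least squares is the natural reading of what is written, but it remains an inference.
- **That the MITRA-on-venous regression has a misleading CI.** SAP 9.3 states no interval for it; the only stated interval belongs to the Bland-Altman line.
- **That a false concentration-dependent bias will appear.** This would have to come through the slope. At the documents' CV of 50% the slope interval is too narrow, but by less than the interval at the centre, and with little between-participant spread it is too wide.
- **That limits of agreement are ruled out.** They are not specified; nothing prevents their being drawn.
- **That the plan fails to show that one MITRA sample can replace a venous one.** The exploratory objective in Protocol 3.3 is to compare PK by the two methods; it does not claim interchangeability.
- **That the phrase "true measurement (average of MITRA dried blood with venous plasma" is an analysis error.** The SAP defines it as the average, which is the usual horizontal axis. The label is loose, but no number changes.

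**Conclusion.** The concern holds in a limited form. SAP 9.3 does not say how up to 11 pairs per participant are handled in the Bland-Altman line, and it specifies no limits of agreement. Under pooled least squares, the 90% CI at the centre of the line is too narrow for any positive rho, covering about 76% at rho 0.1, 60% at 0.3 and 50% at 0.5. This rests on an assumed rho, a common correlation among a participant's pairs and a full set of 11 pairs; fewer usable pairs would reduce the factor. No firm claim is made about the slope. Severity is minor.

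Separately, the documents disagree on whether MITRA covers metabolites. Protocol 9.2.1 has metabolites sampled by vein only. Protocol 8.2.2.2 lists PSL and metabolites under "Blood samples (venous and MITRA) for PK analysis (relative to PSL morning dose"), and SAP 3.1 and 9.3 plan MITRA metabolite data. A reader might conclude that the outputs should simply be limited to PSL, but the passages conflict and do not settle it.

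**What to change.** In SAP 9.3:

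1. State that the Bland-Altman line, and any interval reported for the MITRA-on-venous regression, is fitted with a random participant effect or with participant-clustered standard errors.
2. Report the mean log-difference, back-transformed as a MITRA-blood to plasma ratio, with 95% limits of agreement: exp(mean difference +/- 1.96*sqrt(between-participant variance + within-participant variance)).
3. Optionally, label the horizontal axis as the average of the two methods.
4. Reconcile Protocol 9.2.1 with Protocol 8.2.2.2 and SAP 3.1 and 9.3 on MITRA sampling of metabolites, so that the analytes covered by these outputs are clear.

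The cost of items 1 to 3 is SAP wording and a little extra code, with no new samples or visits. Where differences correlate within participant, the reported interval at the centre of the line becomes wider.
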